2.3 Intended Use / Indications of the Study Product

Synthetic hybrid-scale fiber matrix (Restrata) received FDA 510(k) clearance effective April 26, 2017 (K170300). It is a sterile, single use product intended for use in local management of wounds. It is a soft, white, conformable, non-friable, absorbable matrix that acts as a protective covering for wound defects, providing a moist environment for the body's natural healing process to occur. Synthetic hybrid-scale fiber matrix is a synthetic electrospun matrix that possesses a hybrid-scale fiber architecture similar to native extracellular matrix (ECM), indicated for use in the local management of wounds. The mechanism of action allows for cellular ingrowth and neovascularization before completely degrading via hydrolysis. Synthetic hybrid-scale fiber matrix is made from synthetic biocompatible materials. The product permits the ingress of cells and soft tissue formation in the defect space / wound bed. The product does not contain any human or animal materials or tissues.

Synthetic hybrid-scale fiber matrix is supplied terminally sterile, in a single use double peel package in a variety of sizes. It may be fenestrated or meshed with a scalpel prior to application. Synthetic hybrid-scale fiber matrix must be fenestrated prior to use in any wound prone to exudate in order to permit effective exudate management. Contents of the package are guaranteed sterile and non-pyrogenic unless the package has been opened or damaged.

Synthetic hybrid-scale fiber matrix is intended for use in the management of wounds, including: partial and full thickness wounds, pressure sores/ulcers, venous ulcers, diabetic ulcers, chronic vascular ulcers, tunneled/undermined wounds, surgical wound (e.g., donor site/ grafts, post-laser surgery, post-Mohs surgery, podiatric wounds, wound dehiscence), trauma wounds (e.g., abrasions, lacerations, partial thickness burns, skin tears), and draining wounds. Synthetic hybrid-scale fiber matrix will be used for patients with a DFU(s) or VLU(s).

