5.10 Study Treatment Period - For synthetic hybrid-scale fiber matrix and comparison products

Patients will have weekly visits for up to 12 weeks for patients with DFUs and up to 16 weeks for patients with VLUs (the window for all of these visits is ± 3 days). Assessment and imaging of the wound(s) will occur at each weekly visit unless the visit is conducted virtually (optional for Weeks 5 and 9). Assessment of adverse events and medications will be occur during each weekly visit.

Study product will be re-applied:

- **DFU patients:**
 - **Randomized to Restrata: Biweekly (weeks 2, 4, 6, 8, 10, and 12)**
 - **Randomized to Standard of Care: Weekly**

- **All VLU patients: Biweekly (weeks 2, 4, 6, 8, 10, 12, 14 and 16)**

If 100% re-epithelialization of all study wounds is confirmed before 12 weeks for DFU patients or before 16 weeks for VLU patients, then weekly visits shall cease.

5.10.1 The **evaluator** will complete these assessments at each in-person weekly visit during the Treatment Period:

- Review of images and documentation of 100% re-epithelialization, if present

5.10.2 Personnel will administer the Quality of Life - SF-36 Questionnaire and the pain scale at the following time-point (whichever occurs first):

- When complete wound re-epithelialization of all wounds is first identified, OR
- At Week 12 for DFU patients, OR
- At Week 16 for VLU patients

5.10.3 Personnel will complete the following assessments at each weekly in-person visit:

- Assessment of wound(s) through gross observation and analysis, wound progression, and tissue healing. Gross observation will be utilized to determine the necessity of standard dressing change. Carefully assess the wound(s) for signs of infection, description of exudate present, and wound bed characteristics.
- Assessment of adverse events and medications
- Debridement and dressing changes may occur at each weekly visit or as needed.
 - Debride the wound(s) as needed while not disrupting healing tissue.

- The clinician will inspect the wound bed for signs of infection and healing; the secondary dressing is changed as appropriate with a nontoxic solution. Frequency of secondary dressing changes will be dependent upon the volume of exudate produced, type of dressing used and the clinician's decision upon inspection of the wound(s).

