- Measurement and imaging of wound area via the eKare inSight platform according to the eKare inSight instructions. If debridement is completed during this visit, then the assessment must be completed after debridement.

5.10.4 Reapplication of the study product by personnel will occur:

- **DFU patients:**
 - **Randomized to Restrata: Biweekly up to 12 weeks**
 - **Randomized to Standard of Care: Weekly up to 12 weeks**
- **All VLU patients: Biweekly up to 16 weeks**

If 100% re-epithelialization is confirmed before 12 weeks for DFU patients or before 16 weeks for VLU patients, then re-application shall cease. For patients with more than one wound randomized to the study, re-application of product to each wound shall cease when 100% re-epithelialization of that wound is confirmed. The following will be completed by qualified personnel:

- Evaluate the amount of study product remaining in the wound.
- If the study product is completely intact (no resorption has occurred) and the wound is clean and clear of infection, then leave the product in place.
- The study product should be reapplied over previously absorbed material.
- If any of the study product material has resorbed, then evaluate for additional debridement prior to replacement with new study material.
- In the event the material does need to be removed from the wound bed prior to reapplication, use warm (37°C) sterile saline to continuously rinse the wound site to help detach the material, so as not to cause further damage to the wound bed. Forced removal may result in wound re-injury.

NOTE: If excess exudate collects under Synthetic hybrid-scale fiber matrix, the material should be thoroughly fenestrated to allow the exudate to drain.

5.11 3D Wound Measurement with the eKare inSight Platform

Wounds will be measured using the eKare inSight platform weekly from the beginning of the run-in period until 12 weeks for DFU patients or 16 weeks for VLU patients (except Weeks 5 and 9 if conducted virtually). If 100% re-epithelialization of all wounds is confirmed before 12 weeks for DFU patients or before 16 weeks for VLU patients, then

measurements shall cease. Qualified personnel who are trained on the system will be required to complete the assessment. **If debridement is completed at the visit, then the measurement must occur after debridement.**

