9.5.5 Secondary Endpoints

The following secondary endpoints will be summarized for exploratory purposes. There are no plans for statistical testing of secondary endpoints.

Decrease in Wound Area from Baseline

The difference in wound area from baseline to each time point will be summarized for each treatment group in each arm. The difference in mean percent change in size between the treatment group and control group will be calculated for each timepoint. Wound area measurements will be made via the eKARE inSight system every week (except during virtual visits) for 12 weeks for DFU patients and 16 weeks for VLU patients (except during virtual visits), or until 100% re-epithelialization, whichever occurs first.

Time to Wound Closure

The time to wound closure will be summarized by proportion of patients with wound closure at each timepoint for each treatment group in each arm. The difference in proportion of patients with wound closure between the treatment group and control group will be calculated for each timepoint. Persistence of wound closure will be verified via confirmatory visit within 2 weeks after complete closure has been first determined.

Number of Product Applications

The number of product applications will be summarized for each treatment group in each arm. The difference in mean number of applications between the treatment group and control group will be calculated for each timepoint. Product applications will be defined as the number of product applications prior to complete wound closure within the treatment period for each study arm.

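### Section 5.10.4 tells staff to leave an intact product in place, while Sections 5.10, 5.1 and 5.2 fix the reapplication weeks; the rules conflict in every arm, and the resorption test is worded for the matrix

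*Combined protocol and SAP*

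**What the plan says.** Section 5.10 carries the scope line "For synthetic hybrid-scale fiber matrix and comparison products". It states that study product will be re-applied on these schedules:

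- DFU, matrix: "Randomized to Restrata: Biweekly (weeks 2, 4, 6, 8, 10, and 12").
- DFU, SOC: "Randomized to Standard of Care: Weekly".
- VLU, both groups: "All VLU patients: Biweekly (weeks 2, 4, 6, 8, 10, 12, 14 and 16").

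The schedules of events in Sections 5.1 and 5.2 mark the same weeks. The stated reasons for not re-applying are confirmed complete re-epithelialization (Sections 5.10 and 5.10.4) and, for SOC only, a virtual visit at Week 5 or 9 (Section 5.1 note 3 and Section 5.12).

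Section 5.10.4 opens by naming the same groups and intervals. It then gives one set of steps, with no arm named, to be completed by qualified personnel. They judge how much study product remains, and the next instruction reads: "If the study product is completely intact (no resorption has occurred) and the wound is clean and clear of infection, then leave the product" there. The later steps cover reapplying over absorbed material, considering debridement if any material has resorbed, and rinsing with warm saline if material must be removed.

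Section 2.3 describes the matrix as absorbable, supporting tissue ingrowth "before completely degrading via hydrolysis". Section 2.4.1 describes SOC as debridement, a non-adherent primary dressing and off-loading. Section 2.4.2 describes the skin substitute as living cells with a collagen lattice and gives no resorption property for it.

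**The concern.** Two instructions in the current text give different treatment at the same visit. On the fixed-week reading, every scheduled visit before closure yields an application. On the conditional reading, a visit with an intact product and a clean, uninfected wound does not. Nothing says which prevails.

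Three things depend on the answer:

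- **Delivered treatment.** The primary comparison in each arm of the study is between two treatments whose application frequency is not settled.
- **Deviations.** On the fixed-week reading, a product left in place is a deviation to be reported under Section 7. On the conditional reading, it is compliance. Section 9.2 removes patients with a major violation affecting primary effectiveness from the per-protocol population, so membership of that population may depend on the reading.
- **The applications endpoint.** Section 9.5.5 says "Product applications will be defined as the number of product applications prior to complete wound closure" within the treatment period. The count would mix sites that apply at every scheduled visit with sites that apply conditionally.

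The resorption test adds a further difficulty. It fits the one product described as absorbable. For a dressing or the skin substitute, the protocol text gives staff no way to interpret it.

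**Working it through.** **1. Passages side by side**

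| Question | Sections 5.10, 5.1, 5.2 | Steps in Section 5.10.4 |
|---|---|---|
| Who is covered? | Matrix, SOC, both VLU groups | The same groups are listed above the steps; no step names an arm |
| When is product re-applied? | At listed weeks, or weekly for SOC | Depends on whether product is intact and on the state of the wound |
| What excuses a scheduled application? | Confirmed closure; for SOC, a virtual Week 5 or 9 | Also an intact product on a clean, uninfected wound |

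The last row is the contradiction. It is not confined to the control groups, because the matrix has fixed weeks too.

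**2. Scheduled maxima, counting Week 0**

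- DFU matrix: Weeks 0, 2, ..., 12 = 12/2 + 1 = 7.
- DFU SOC: Weeks 0 to 12 = 13, or 13 − 2 = 11 if Weeks 5 and 9 are both virtual.
- Each VLU group: Weeks 0, 2, ..., 16 = 16/2 + 1 = 9.

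These are ceilings under the fixed-week reading. The documents do not allow a count under the conditional reading.

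**3. The plan's sample sizes are unaffected**

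Inputs are from Sections 9.3.1 and 9.3.2: margin 0.10, one-sided alpha 0.05, power 0.80. The Farrington–Manning formula is n = [(1.645·s0 + 0.842·s1)/(p1 − p2 + 0.10)]². Here s0 uses rates restricted to the margin and s1 uses the assumed rates.

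- DFU (75% vs 60%): restricted rates 0.616 and 0.716 give n = 43.1, so 44 per group; 88/0.80 = 110.
- VLU (75% vs 50%): restricted rates 0.566 and 0.666 give n = 23.1, so 24 per group; 48/0.80 = 60.

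Both match the plan.

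**4. Which way could it bias the comparison?**

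Set the true difference at the margin: 50% vs 60% in DFU with 44 per group, 40% vs 50% in VLU with 24 per group. The rejection probability is the sum of the two binomial probabilities over all outcomes with Z > 1.645, where Z is the Farrington–Manning statistic at −0.10. Suppose under-delivery costs the affected group 5 points of closure. That figure is an assumption with no source in the documents, used only to show the sign.

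| Group affected | DFU | VLU |
|---|---|---|
| Neither | 4.6% | 4.5% |
| Control only | 11.2% | 9.0% |
| Both equally | 4.6% | 4.6% |
| Matrix only | 1.5% | 2.0% |

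The sign depends entirely on which group is affected, and the documents do not settle that.

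**The case against.** The strongest defence is that the steps were meant for the matrix alone. Their vocabulary is of resorption and absorbed material, and the note that closes Section 5.10.4 names the matrix. Section 1 lists only the matrix as study product and puts SOC and the skin substitute under comparators. This is a plausible account of intent, but it does not settle the text. Sections 5.10 and 5.10.4 use the same term for SOC and all VLU patients, and the steps follow that list without restriction. Even if it is accepted, the conflict with the fixed weeks remains for the matrix.

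A reader might infer that control could be reduced to little more than the initial application. The documents do not support that.

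- **SOC.** Each in-person weekly visit includes wound inspection and imaging, which is hard to square with a dressing left on from Week 0. Section 5.10.3 permits dressing changes at each weekly visit. Section 5.12 allows SOC reapplication to be forgone at a virtual visit only if the investigator judges this to be in the patient's interest, so weekly reapplication is the default.
- **Skin substitute.** Section 5.9.2 refers to the instructions for use in Appendix C. Their text is not available here and counts neither way.

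A reader might also infer that the conflict tilts the trial toward non-inferiority. That holds only if control alone is under-delivered. Section 2.1 says a wound matrix should persist for at least three weeks, so an intact matrix at a two-week check is plausible and its reapplication could be withheld too.

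It is also fair to say that the applications endpoint is exploratory and untested, and that Section 9.5.5 already summarizes it by group. That limits the harm. But a total by group does not show whether fewer applications reflect earlier closure, a missed visit or a product left in place.

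**Conclusion.** The point stands as an internal contradiction affecting every arm. Fixed reapplication weeks and a leave-in-place instruction are both in force, and the condition is worded for the only product the protocol describes as absorbable. What is delivered against schedules of 13 (or 11), 7 and 9 applications, what is a deviation, possibly who is in the per-protocol population, and what the applications endpoint counts all depend on the site's reading.

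The effect on the primary result cannot be sized from the documents, and its direction is unknown. The primary mITT population is defined by at least one application, so its membership does not turn on this point. No sample-size or power figure is wrong because of it. The conclusion rests on the wording alone. It assumes nothing about how sites behave or about what the appended instructions for use say.

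**What to change.** - Reconcile Section 5.10.4 with Section 5.10 and the tables in Sections 5.1 and 5.2.
- Label each step in Section 5.10.4 (resorption check, leaving in place, reapplying over absorbed material, saline removal) with the product it governs.
- State for each arm whether the listed weeks are mandatory or conditional. Which it should be is a clinical decision for the sponsor and investigators; this review takes no position.
- Say whether a product left in place at a scheduled visit is a protocol deviation and, if so, whether it bears on per-protocol membership.
- At each scheduled application visit, record whether product was applied or left in place, with the reason.
- Report delivered against scheduled applications by arm.

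The cost is protocol wording, one eCRF field and one descriptive table. No extra visits or staff are needed.

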5.13 Two Week Visit to Confirm Wound Closure

An in-person visit with the patient to confirm 100% re-epithelialization will be completed two weeks (± 3 days) following the visit when 100% re-epithelialization was first identified and documented. A clinic visit is NOT required if there is not complete wound re-epithelialization of any wound at 12 weeks or earlier for DFU patients (or 16 weeks or earlier for VLU patients). For patients with more than one wound, an in-person follow-up visit will be completed two weeks following 100% re-epithelialization of each wound.

Research personnel will complete the following:

- Measurement and imaging of wound area via the eKare inSight platform according to the eKare inSight instructions.
- Wound drainage since the previous visit
- Additional dressing changes since the previous visit
- Adverse events
- Review wound imaging to confirm the wound remains closed

5.14 Six-Month Telephone Call

For patients with 100% re-epithelialization of at least one wound, a telephone call with the patient will be completed six-months (± 30 days) after Week 0. The following information will be collected:

- Confirmation of whether wound(s) remains closed
- Wound drainage since the previous visit
- Additional dressing changes since the previous visit
- Adverse events

A telephone call is not required if complete wound re-epithelialization of at least one study wound does not occur at or before 12 weeks for DFU patients, or at or before 16 weeks for VLU patients.

5.15 Study Exit

5.15.1 Study Participation Exit Points

A patient's participation in the study will end after any of the following:

- DFU patients without 100% re-epithelialization of at least one study wound: at 12 weeks
- VLU patients without 100% re-epithelialization of at least one study wound: at 16 weeks

- Completion of six-month telephone call (for patients with 100% re-epithelialization of at least one study wound)
- Patient withdrawal
- The Investigator may withdraw the patient if he/she determines it is in the patient's best interest
- Patient lost to follow-up
- Amputation of all or part of the study limb
- Closure of study
- Patient death

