5.5 Run-In Period

A 2-week run-in period will be required prior to enrollment/randomization and treatment in order to complete screening assessments and confirm that the wound(s) has not decreased in size by more than 30%. Written informed consent must be obtained prior to or at the beginning of the run-in period.

More than one wound per patient may be screened, enrolled and randomized to a study product. All wounds screened/enrolled must be either DFUs or VLUs. A patient may not have both a DFU and VLU that are screened and randomized to a study product. If more than one wound is enrolled, then the wounds must be at least 3 cm apart. Additionally,

the run-in period will begin on the same day for all wounds. A patient may not have a separate run-in period for each wound.

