5.15.2 Patient Withdrawal

A patient (or patient's LAR) may choose to withdraw from the study at any time without penalty or loss of benefits. The patient should notify the investigator (or designee) of his/her desire to withdraw, and the investigator (or designee) should ask for and document the reason for withdrawal. The investigator may also choose to withdraw a patient from the study at any time if he/she considers it to be in the patient's best interest. The reason for withdrawal should be recorded. Any data collected on the patient up to the point of withdrawal may be used in the study.

If complete wound closure has not been confirmed at the time of withdrawal from the study, then the investigator should attempt to determine the status of the wound at the time of the patient's withdrawal to the best of the patient's ability (i.e., healed, not healed, seeking additional treatment, not seeking additional treatment) and to complete as many of the patient-reported outcomes questionnaires as the patient is able and willing to complete.

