6. ADVERSE EVENTS (AE)

6.1 Principal Investigator Responsibilities

The investigator (or designee) should record and maintain all adverse events that occur over the course of the patient's participation in the study (randomization through study exit) during or outside of study visits. Adverse events that are reported to the sponsor will be assessed by an investigator. Adverse event assessments should include severity, seriousness, and relatedness to the product, study procedures and pre-existing conditions. See Section 6.4 for adverse events that are required to be reported to the Sponsor.

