6.4 Adverse Event Reporting

The following adverse events are required to be promptly reported to the sponsor on the adverse event eCRF:

- Any serious adverse event whether or not it is related to a study product/procedure
- Any adverse event that in the opinion of the investigator is definitely related, probably related, or possibly related to a study product and/or study procedure
- The following adverse events whether or not they are related to a study product/procedure:
 - Infection of wound and/or area surrounding wound
 - Complete or partial amputation of lower extremity
 - Allergic reaction to a study product
 - Excessive redness, pain, swelling or blistering of wound

Serious adverse product effects should be reported to the sponsor as soon as possible. Pre-existing conditions or adverse events that occur prior to randomization are not required to be reported.

The investigator (or designee) is also required to report AEs to the IRB/EC if the AEs are required to be reported per the IRB/EC reporting requirements.

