9.5.7 Adverse Events

9.5.7.1 All Adverse Events

Summaries of incidence rates of individual AEs overall will be prepared. Only treatment emergent AEs will be analyzed (a treatment emergent adverse event is one that started or worsened in severity at or after start of randomized treatment). Because a patient may experience more than one AE, summaries will provide both the number of patients experiencing at least one event and the number of events within a reporting period. Percentages provided will be the percent of patients experiencing one or more adverse events. In addition, incidence of AEs will be presented by severity (mild, moderate, severe) and by relationship to investigational product or procedure. Patients experiencing an event more than once will be counted under the maximum severity/relationship experienced.

A listing of all adverse events will include the patient number, AE number, days since index procedure, the AE name, the severity of AE, whether or not the AE is classified as serious (SAE), the relationship of the AE to the study product or procedure, the action taken, and the outcome.

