9.5.7.3 Adverse Events of Interest

Summaries of incidence rates of the following AEs by treatment group will be prepared:

- Infection of wound and/or area surrounding wound
- Amputation of lower extremity
- Allergic reaction
- Excessive redness, pain, swelling or blistering of wound

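### Amputation on the study limb ends all follow-up of the patient, and the plan assigns no endpoint status to an unhealed study wound removed by it

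*Combined protocol and SAP*

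**What the plan says.** **Exit.** Section 5.15.1 lists the events that end a patient's participation. One is "Amputation of all or part of the study limb". The rule acts on the patient, not the wound. It makes no exception for a partial amputation that leaves a study wound in place, or for safety follow-up.

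**AE window.** Section 6.1 has AEs recorded over "randomization through study exit".

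**Amputation as an AE.** Section 6.4 requires reporting, whether or not related, of "Complete or partial amputation of lower extremity". Section 9.5.7.3 summarises "Amputation of lower extremity" by treatment group. The AE listing in 9.5.7.1 includes "the action taken, and the outcome".

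**Later contact.** Section 5.14 states: "For patients with 100% re-epithelialization of at least one wound, a telephone call with the patient will be completed six-months" after Week 0. That call collects AEs and closure status.

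**Several wounds.** Section 5.5 states: "More than one wound per patient may be screened, enrolled and randomized to a study product". Section 9.5.4 uses the largest study wound for the primary endpoint.

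**Wound status at exit.** Section 5.15.2 asks for it under the condition "If complete wound closure has not been confirmed at the time of withdrawal from the study". Withdrawal and amputation are separate items in 5.15.1.

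**Analysis.** Section 9.2 makes mITT the primary efficacy population, and the per-protocol (PP) set requires primary endpoint data. Section 9.6 imputes missing closure status by logistic multiple imputation from age, gender and variables left to a formal statistical analysis plan. It does not mention amputation.

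**The concern.** Two separate gaps follow.

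The first is stated in the text. Once a limb is amputated in whole or part, the plan stops looking at the patient. Re-amputation, infection or death after that date falls outside AE collection, although amputation is one of the few AEs singled out for reporting and for a by-group summary. A second study wound, or a single ulcer spared because the amputation was elsewhere on the limb, is no longer assessed. If the spared wound is the largest and still open, a primary outcome that could have been observed becomes missing.

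The second is a matter of silence. An unhealed study wound removed by amputation cannot go on to meet the endpoint, yet no rule says so. If the patient is handled as missing under 9.6, a known failure becomes a fractional success in mITT and leaves PP for lack of endpoint data. The distortion would be largest if one product had more amputations than the other, which is when an undistorted comparison matters most.

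**Working it through.** **Inputs**
- DFU (9.3.1): planned closure 75% v 60%, margin 10 points, 44 per group, 110 after 20% loss.
- VLU (9.3.2): planned closure 75% v 50%, margin 10 points, 24 per group, 60 after 20% loss.
- One-sided alpha 0.05, power 0.80, 1:1 allocation.
- The documents give no amputation rate.

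**The plan's own figures.** The Farrington-Manning formula gives 43.1, rounded up to 44 per group for DFU, and 88/0.8 = 110. For VLU it gives 23.1, rounded up to 24, and 48/0.8 = 60. Both reproduce, and neither is in dispute.

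**AE follow-up lost per patient (planned end minus exit week)**
- Unhealed, exit halfway: 12 − 6 = 6 weeks (DFU); 16 − 8 = 8 weeks (VLU).
- Closed wound, exit at the end of the treatment period, with six months taken as 26 weeks: 26 − 12 = 14 weeks (DFU); 26 − 16 = 10 weeks (VLU).

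**Endpoint effect per unhealed amputated patient.** Group sizes are 110/2 = 55 and 60/2 = 30, all assumed to be in mITT. If the patient is imputed with closure probability p instead of scored 0, the group's closure rate rises by p/n.

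| Imputed p (assumption) | DFU, n = 55 | VLU, n = 30 |
|---|---|---|
| Planned control rate | 0.60/55 = 1.1 points | 0.50/30 = 1.7 points |
| Planned matrix rate | 0.75/55 = 1.4 points | 0.75/30 = 2.5 points |
| 0.25 | 0.25/55 = 0.5 points | 0.25/30 = 0.8 points |

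**Net effect on the difference (matrix minus control)**
- One such patient per group, same imputed rate in both: 0.
- One per group at group-specific planned rates: 1.36 − 1.09 = 0.27 points (DFU) and 2.50 − 1.67 = 0.83 points (VLU), both toward the matrix.
- DFU, two per group: imputed 15.0 points; scored as failure, 0.75 × 53/55 − 0.60 × 53/55 = 14.5 points.
- DFU, three matrix and one control: imputed 15.0; scored as failure, 0.75 × 52/55 − 0.60 × 54/55 = 12.0.
- DFU, one matrix and three control: imputed 15.0; scored as failure, 0.75 × 54/55 − 0.60 × 52/55 = 16.9.

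The counts in these examples are illustrations, not estimates. Imputing a matrix patient favours non-inferiority; imputing a control patient works against it.

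**PP.** Dropping one control failure moves 33/55 = 60.0% to 33/54 = 61.1% (DFU), or 15/30 = 50.0% to 15/29 = 51.7% (VLU). That is conservative for the matrix. Dropping a matrix failure would act the other way.

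**The case against.** The strongest reply concerns the endpoint. A reader might infer that the plan imputes an unhealed amputated wound and removes the patient from PP. The documents do not go that far. Section 9.6 applies to missing closure status and never names amputation. The endpoint is closure within 12 or 16 weeks, so a wound imaged as open and then removed could be scored as not closed with nothing missing. The formal statistical analysis plan mentioned in 9.6 is not among the documents and could hold such a rule. This stands: imputation is the likely reading, not the only one, and PP exclusion depends on it.

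The size is also hypothetical. There is no event count, the imputed rate is assumed, and 9.6 does not name treatment group among its predictors. This stands too.

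Eligibility makes early amputation less likely. Both arms require adequate circulation and exclude active wound infection (4.1, 4.2), and DFU patients with osteomyelitis or exposed bone are excluded. This supports a small count, not zero.

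A reader might also infer that the safety record of amputations is lost. It is not: the event is reported, summarised by group, and listed with its outcome. AE analyses are tertiary and descriptive, and unhealed patients leave AE collection at Week 12 or 16 anyway. Where all wounds have closed and the two-week visit is done, the only scheduled contact lost is one telephone call. Among spared wounds, only the largest bears on the primary endpoint.

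None of this answers the exit rule itself. By contrast, 5.15.3 keeps patients in the study after missed visits; amputation gets less follow-up than that.

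**Conclusion.** The point holds in two parts of different strength.

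The loss of later AEs, of the six-month call and of remaining-wound assessment follows directly from 5.15.1 and 6.1. Its main effect is on the completeness of a descriptive safety record, plus an avoidable missing primary outcome when the largest wound is spared and still open.

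The endpoint status of an unhealed amputated wound is unspecified. Imputation and the resulting exclusion from PP are possible consequences of 9.6 as written, not stated rules. If imputation occurs at the planned rates, each such patient moves the group rate by 1.1 to 1.4 points (DFU) or 1.7 to 2.5 points (VLU) against a 10-point margin. The direction depends on the group, and the net effect is near zero if events balance. These figures rest on full groups of 55 and 30 in mITT and on the assumed imputed rate.

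The number of patients is unknown and probably small. The change is worth making because the outcome in question is known and the remedy is cheap. Confidence is medium.

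**What to change.** **Section 5.15.1.** Remove amputation from the patient-level exit points. Stop study product only on a wound removed by the amputation. Let product and scheduled assessment continue on any remaining study wound at the investigator's discretion, including when the amputation was elsewhere on the limb. Section 5.10.4 already stops product wound by wound after closure.

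**AE follow-up.** Unless consent is withdrawn, collect AEs to the patient's planned end: Week 12 (DFU), Week 16 (VLU), or the six-month call if a wound had closed. If no study wound remains, at least one telephone contact at that point is enough; weekly contacts are not needed. Remote contact is now provided for only at Weeks 5 and 9 and at six months (5.12, 5.14), so one sentence must allow it at Week 12 or 16.

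**Section 9.6.** Score a study wound amputated before confirmed closure as not closed, without imputation, in both mITT and PP. The patient then has endpoint data and is not dropped from PP for lacking it.

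**Cost.** Amendment wording, one eCRF field and a few contacts per affected patient, with clinic visits only if a study wound remains. The sample size is unchanged.
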